### **Surgical Procedure and Intervention**

#### **Cytoreductive Surgery and Peritonectomy**

All patients underwent CRS performed by experienced surgical oncologists following standardized institutional protocols. The goal of CRS was complete or near-complete macroscopic tumor clearance (CC-0 or CC-1 resection). Peritonectomy procedures were carried out as required based on disease distribution and included parietal and/or visceral peritoneal stripping.

The use of HIPEC was permitted and performed according to tumor-specific protocols but was evenly distributed between study arms.

### **Intervention Group: HPTC Peritoneal Reconstruction**

In patients randomized to the intervention arm, peritoneal defects created following peritonectomy were reconstructed using HPTC (Surgicoll-Mesh®), a sterile, resorbable, high-purity Type I collagen scaffold. The mesh was tailored intraoperatively to match the dimensions of the peritoneal defect and secured using interrupted absorbable sutures to adjacent tissue margins prior to abdominal closure.

The biomaterial was applied without tension and without overlap onto visceral organs.

The mesh was intended to function as a temporary biologic barrier and regenerative scaffold, facilitating organized tissue remodeling during the early postoperative period [9–11].

### **Control Group: Standard Peritonectomy Closure**

Patients allocated to the control arm underwent standard peritonectomy closure without the use of any peritoneal substitute or biomaterial. Peritoneal defects were left untreated, allowing secondary healing according to standard institutional practice.

### **Postoperative Care and Follow-Up**

Postoperative management protocols, including analgesia, antibiotic prophylaxis, early mobilization, and nutritional advancement, were standardized across centers. Nasogastric decompression was discontinued at the discretion of the treating team based on bowel function recovery.

Patients were followed for a minimum of two months postoperatively, with scheduled clinical assessments at discharge, 30 days, and 60 days. Imaging studies and quality-of-life assessments were performed according to protocol-defined timelines.

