#### **Secondary Outcomes**

Secondary outcomes included:

- Individual complication rates, including intraperitoneal adhesions, bowel obstruction, surgical site infection, incisional hernia, and fistula formation

- Time to bowel function recovery, defined as the time to first flatus and tolerance of oral diet
- Length of intensive care unit (ICU) stay and total hospital stay
- Device-related adverse events, including infection, inflammatory reaction, or mesh-related complications
- Radiologic assessment of adhesions or obstruction using magnetic resonance imaging (MRI) at baseline, one month, and two months
- Quality of life assessment using the European Organisation for Research and Treatment of Cancer Quality of Life Questionnaire Core 30 (EORTC QLQ-C30), a validated cancer-specific instrument [20]

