### Statistical Analysis Plan

Statistical analyses were performed using SPSS version 29.0 (IBM Corp., Armonk, NY, USA). Continuous variables were assessed for normality using the Shapiro–Wilk test and are presented as mean  $\pm$  standard deviation for normally distributed data or median with interquartile range for non-normally distributed data. Between-group comparisons were conducted using the independent t-test or Mann–Whitney U test for continuous variables and the chi-square test or Fisher’s exact test for categorical variables, as appropriate. Effect estimates for the primary and key secondary binary outcomes were expressed as relative risks with 95% confidence intervals. Time-to-event outcomes, including time to bowel function recovery, were analyzed using Kaplan–Meier survival curves with log-rank testing. Multivariable logistic regression analysis was performed to adjust for potential confounders, including age, primary tumor type, peritoneal cancer index score, and use of hyperthermic intraperitoneal chemotherapy. All statistical tests were two-sided, and a p-value  $< 0.05$  was considered statistically significant. Analyses were conducted on an intention-to-treat basis.

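### No baseline or sampling days are stated for QLQ-C30, and the planned unadjusted test gives up precision that ANCOVA on a preoperative score would recover

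*Combined protocol and SAP*

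**What the plan says.** All references are to the combined protocol and SAP.

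- **Postoperative Care and Follow-Up.** Patients are followed for at least two months "with scheduled clinical assessments at discharge, 30 days, and 60 days. Imaging studies and quality-of-life assessments were performed according to protocol-defined timelines". No section sets out a timeline for quality of life.
- **Secondary Outcomes.** The imaging item has explicit times: "Radiologic assessment of adhesions or obstruction using magnetic resonance imaging (MRI) at baseline, one month, and two months". The item after it reads "Quality of life assessment using the European Organisation for Research and Treatment of Cancer Quality of Life Questionnaire Core 30" and gives no baseline, day, window, scale or summary measure.
- **Statistical Analysis Plan.** "Between-group comparisons were conducted using the independent t-test or Mann–Whitney U test for continuous variables". The only covariate-adjusted model is a logistic regression on age, tumor type, peritoneal cancer index and HIPEC use. Baseline quality of life is not among the covariates, and no change-score, ANCOVA or repeated-measures analysis is described.
- **Randomization and Allocation.** The envelope is opened during surgery, once cytoreduction is complete.

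**The concern.** Quality of life is a declared secondary objective, yet the plan does not say when it is measured, whether there is a preoperative score, or which scale is compared. The reference to timelines leads to nothing in the document. The analysis section, read as it stands, makes no use of a baseline score even if one exists.

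What is at stake is mainly precision. The Study Population section admits five tumor types and ECOG 0–2, so preoperative quality of life can be expected to vary widely. In a trial of 30 per arm, a preoperative score is the obvious covariate for removing part of that variation and for seeing whether the arms started level. It cannot be collected afterwards.

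A second, conditional matter follows from the open schedule. Nothing prevents a questionnaire at discharge, and length of hospital stay is itself compared between arms. Scores taken at discharge could therefore come from different postoperative days in the two arms.

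**Working it through.** The plan gives no SD, target difference or precision for QLQ-C30, so there is no figure of its own to reproduce.

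**Inputs**
- 30 patients per arm (Sample Size Calculation), all assumed to have a score.
- Two-sided 5% level (Statistical Analysis Plan).
- SD of 22 points: an assumption. Results are also given in SD units so that another value can be substituted.
- Correlation r between preoperative and postoperative score of 0.3, 0.5 or 0.7: an assumption, shown as a range.

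**Step 1: width of the interval**

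Half-width = 1.96 × SD × √(2/30) × √(1 − r²), with √(2/30) = 0.2582. The unadjusted comparison is r = 0: 1.96 × 22 × 0.2582 = 11.1 points. The formula ignores the one degree of freedom spent on the covariate.

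| r | 1 − r² | Half-width (SD units) | Half-width (points, SD 22) | Equivalent sample size, 1/(1 − r²) |
|---|---|---|---|---|
| none | 1.00 | 0.506 | 11.1 | 1.00 |
| 0.3 | 0.91 | 0.483 | 10.6 | 1.10 |
| 0.5 | 0.75 | 0.438 | 9.6 | 1.33 |
| 0.7 | 0.51 | 0.361 | 8.0 | 1.96 |

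**Step 2: detectable difference and power**

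At 80% power the detectable difference is (1.96 + 0.842) × 0.2582 = 0.72 SD without a baseline. Multiplying by √(1 − r²) gives 0.69, 0.63 or 0.52 SD. For an assumed true difference of 0.5 SD, power is 49% unadjusted and 53%, 61% or 77% adjusted.

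**Step 3: chance imbalance**

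The standard error of a baseline difference between arms is √(2/30) = 0.26 SD. The probability that it exceeds 0.3 SD in either direction is 2 × [1 − Φ(0.3/0.2582)], about 25%. At SD 22, an imbalance of 0.3 SD is 6.6 points. It moves the unadjusted postoperative difference by r × 6.6, which is 2.0, 3.3 or 4.6 points at the three correlations (equal SD before and after surgery assumed). This is not additional to Step 1, because the 11.1-point half-width already includes it. Adjustment is what removes it.

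**The case against.** The strongest reply is that this is a gap in specification and not a shown defect. Three stronger readings are tempting, and the documents support none of them.

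- **A reader might infer that no preoperative score was taken.** The text says only that timelines existed and does not give them. MRI is scheduled "magnetic resonance imaging (MRI) at baseline, one month, and two months", which I read as including a contact before surgery, and a questionnaire there cannot be ruled out. What can be said is that no baseline is specified.
- **A reader might infer that QLQ-C30 is compared at discharge and is therefore confounded with time since surgery.** Discharge appears in the sentence on clinical assessments. Quality of life is in a separate sentence, paired with imaging, whose listed times do not include discharge. The hazard exists only if a discharge questionnaire was used. Its size is unknown: assumed recovery of 0.5 to 2 points per day and an assumed gap of 1 to 5 days between arms would give anything from 0.5 to 10 points.
- **A reader might infer bias from the missing baseline.** Allocation is randomized, so an unadjusted comparison on a fixed postoperative day is unbiased in expectation, and its confidence interval already allows for chance imbalance.

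It is also fair to say that the analysis sentence covers continuous variables in general and could be applied to change scores, that the gain is modest at low correlation, and that power for 0.5 SD stays below 80% even at r = 0.7. All of this stands. What remains is that the schedule cannot be found, the scale and time point are not named, and the one stated method for continuous outcomes leaves a cheap gain in precision unused.

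**Conclusion.** The point holds as a cheap improvement to a secondary outcome. QLQ-C30 has no stated baseline, sampling days or scale, the timelines referred to are not in the document, and the stated comparison is unadjusted. The consequence is lost precision and chance imbalance that cannot be adjusted for. It is not bias in a fixed-day comparison.

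If the SD is 22 points and all 30 patients per arm have scores, adjustment would reduce the 95% half-width by about 0.5 points at r = 0.3 (11.1 to 10.6), 1.5 at r = 0.5 (to 9.6) and 3.1 at r = 0.7 (to 8.0). The SD and correlation are assumptions. The relative gain depends on the correlation alone. The primary outcome is unaffected.

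**What to change.** 1. State the QLQ-C30 schedule in the protocol: before surgery, at the same contact as the baseline MRI, and at days 30 and 60 counted from surgery, with windows. A preoperative score always precedes allocation, because the envelope is opened during the operation.
2. In the SAP, name one scale and one time point, for example global health status at day 60 with day 30 as supportive. The choice belongs to the sponsor but must be made in advance.
3. For QLQ-C30, replace the unadjusted t-test or Mann–Whitney test with ANCOVA on the preoperative score.
4. If any questionnaire is given at discharge, do not use it to compare the arms.
5. The document is written in the past tense, so enrolment may be over. If preoperative scores were collected, say so and use them as the covariate. If they were not, report the day-30 and day-60 comparisons and state that they are unadjusted.

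The cost is one extra 30-item questionnaire per patient at a contact that already takes place, plus SAP wording. A few questionnaires will come from patients who are found unsuitable during surgery and never randomized.

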### **Outcome Measures**

#### **Primary Outcome**

The primary outcome was the incidence of major intra-abdominal complications within two months following surgery. Major complications were predefined as:

- Adhesive small bowel obstruction requiring intervention
- Enterocutaneous fistula
- Reoperation for intra-abdominal complication
- Grade  $\geq 3$  wound complications based on the Clavien–Dindo classification

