## **MATERIALS AND METHODS**

### **Study Design and Setting**

This study was designed as a prospective, multicenter, open-label, randomized controlled clinical trial evaluating the safety and efficacy of a high-purity Type I collagen-based biomaterial (Surgicoll-Mesh®) as a peritoneal substitute following peritonectomy in patients undergoing cytoreductive surgery (CRS) for intraperitoneal malignancies. The trial was conducted at two tertiary referral centers specializing in oncologic and reconstructive surgery.

The trial was conducted at two tertiary oncology referral centers – JSS Academy of Higher Education and Research, Mysuru and Adichunchangiri Institute of Medical Sciences, B G Nagara. The trial was registered prospectively with ClinicalTrials.gov (ID: NCT07241091) and approved by the Institutional Ethics Committee (Approval No.: AIMS/IEC/266/2025). The study was conducted in accordance with the principles of the Declaration of Helsinki, Good Clinical Practice (GCP) guidelines, and Consolidated Standards of Reporting Trials (CONSORT) recommendations [18].

Institutional Ethics Committee approval was obtained at all participating centers prior to patient enrollment.

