### **Randomization and Allocation**

Eligible patients were randomized in a 1:1 ratio to either the intervention group (HPTC peritoneal reconstruction) or the control group (standard peritonectomy closure). Randomization was performed using a computer-generated block randomization sequence with variable block sizes to ensure balanced group allocation across participating centers.

Allocation concealment was achieved using sealed, opaque envelopes opened intraoperatively after completion of cytoreduction and confirmation of peritoneal defect suitability. Due to the nature of the surgical intervention, blinding of the operating surgeon was not feasible. However, outcome assessors, radiologists evaluating imaging studies, and statisticians were blinded to treatment allocation wherever applicable.

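### Two of the four primary components, and mostly a third, count only after a decision to intervene in an open-label trial, so blinded assessors cannot remove a between-arm difference in the threshold for intervening

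*Combined protocol and SAP*

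**What the plan says.** All references are to the combined protocol and SAP.

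- **Primary Outcome.** "The primary outcome was the incidence of major intra-abdominal complications within two months following surgery". The four components are "Adhesive small bowel obstruction requiring intervention", "Enterocutaneous fistula", "Reoperation for intra-abdominal complication" and, at grade 3 or higher, "wound complications based on the Clavien–Dindo classification". The section does not define intervention and gives no criteria for intervening or reoperating.
- **Study Design and Setting.** "This study was designed as a prospective, multicenter, open-label, randomized controlled clinical trial".
- **Randomization and Allocation.** The plan accepts that "blinding of the operating surgeon was not feasible" and offers as its safeguard that "outcome assessors, radiologists evaluating imaging studies, and statisticians were blinded to treatment allocation wherever applicable". It does not say which judgements the assessors make.
- **Postoperative Care and Follow-Up.** The care listed as standardised is analgesia, antibiotics, mobilisation and nutrition. Re-intervention is not on the list.
- **Secondary Outcomes.** Bowel obstruction and fistula appear with no intervention condition. MRI for adhesions or obstruction is scheduled at baseline, one month and two months.

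**The concern.** An outcome assessor works on a record that already exists. Blinding prevents a slanted reading of that record, but it has no hold on a decision made earlier by clinicians who know whether a mesh is in place. Two patients with the same partial obstruction score differently if one is observed and the other is re-explored. A team might hesitate to reopen over a new implant, or might reopen sooner out of worry about it, so a difference could run either way.

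Attribution is a second, smaller gap. Cytoreductive Surgery and Peritonectomy describes complete or near-complete clearance as a goal, and no section makes it a condition of randomisation. Some randomised patients may therefore have residual tumour, and whether an obstruction is adhesive becomes a judgement. The plan does not say who makes it.

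At stake is how the primary comparison is read. The arms could differ because intervention thresholds differed, with no difference in the underlying complications.

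**Working it through.** **Step 1. Does each component need a decision to intervene?**

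| Component | Needs a decision? | Basis |
|---|---|---|
| Obstruction | Yes | Its own wording |
| Enterocutaneous fistula | No | A clinical finding |
| Reoperation | Yes | The event is the decision |
| Wound complication, grade 3 or higher | Mostly | The named scale, taken here to grade mainly by treatment given; the plan does not set out the grades |

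The count is two by wording and one largely through the scale.

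**Step 2. Where does blinding act?** The order is: complication, decision to intervene, record, assessment. The stated blinding covers the last step. No section describes blinding, or written criteria, for the second.

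**Step 3. How large could the effect be?** The plan gives no figure on this point, so there is none to reproduce. What follows is an illustration.

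Inputs from the plan:
- 30 patients per arm and a 40% control rate (Sample Size Calculation);
- two-sided 5% level, chi-square or Fisher's exact test (Statistical Analysis Plan).

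Assumptions not in the plan:
- no true effect, with a true rate of 40% in both arms;
- a fraction *f* of all events in the mesh arm is managed without the counted intervention.

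The observed mesh rate is 0.40 × (1 − *f*):
- *f* = 0.15: 0.40 × 0.85 = 0.34, relative risk 0.85;
- *f* = 0.25: 0.40 × 0.75 = 0.30, relative risk 0.75.

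The chance of a significant result favouring the mesh is the sum, over control counts *i* and mesh counts *j* with *i* > *j* and p < 0.05, of Bin(*i*; 30, 0.40) × Bin(*j*; 30, observed mesh rate). For chi-square, z = [(*i* − *j*)/30] / √[p̄(1 − p̄) × 2/30], with p̄ = (*i* + *j*)/60.

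| Observed control / mesh | Chi-square | Fisher |
|---|---|---|
| 40% / 40% | 2.4% | 1.3% |
| 40% / 34% | 6.7% | 4.0% |
| 40% / 30% | 12.1% | 7.7% |

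The arms are the same size, so the calculation is symmetric. If the same shift fell in the control arm, these would be the chances of a significant result against the mesh.

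**Step 4. What would the shift require?** Fistula is exempt. If, by assumption, 75% of events depend on a decision, *f* = 0.25 means 0.25/0.75 = one third of those events, and *f* = 0.15 means 0.15/0.75 = one fifth. A patient with a second qualifying component still counts, so more interventions than this would have to be avoided.

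**Step 5. How sensitive is a single result?** Suppose 12/30 control events.
- 5/30 in the mesh arm: p̄ = 17/60 = 0.283, z = 0.2333/0.1164 = 2.005, p = 0.045.
- 6/30 in the mesh arm: p̄ = 18/60 = 0.30, z = 0.2000/0.1183 = 1.69, p = 0.091.

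Near that boundary, one patient managed differently changes the chi-square conclusion. Fisher's test needs 4/30 or fewer.

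**The case against.** Requiring an intervention is a legitimate way to define a major complication, and the plan contains no contradiction or miscalculation here. That stands, and it is why the composite should stay primary.

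The plan also has partial safeguards. Obstruction and fistula are secondary outcomes with no intervention condition, and radiologists are blinded when reading imaging. That stands too. What is missing is a combined, pre-specified version to set beside the primary outcome.

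The illustration can be challenged. The 15% and 25% shifts have no source in the plan, the table shows one direction, and the 40% is introduced as a rate of postoperative complications in general, not of this composite. All of this is correct. The figures show scale and do not estimate bias.

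Two stronger readings are tempting, and the documents do not support them:
- A reader might infer that three components occur only when the treating surgeon chooses to act. Two do by wording. The third rests on a scale whose grades the plan does not define. The plan names the operating surgeon as unblinded but does not say that this person makes every postoperative decision. An unblinded treating team is the natural reading of an open-label design, not a stated fact.
- A reader might infer that the unblinded team decides whether an obstruction is adhesive. The plan does not say who decides, and the blinded assessors could do it.

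**Conclusion.** The concern holds in a limited form. Two primary components depend on a decision to intervene by their own wording, and a third mostly does through its scale. In an open-label trial with no stated intervention criteria and no blinded decision-maker, assessor blinding cannot remove a difference in threshold between arms.

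It would go too far to conclude that blinding fails to protect the primary outcome at all. It still protects fistula, and it protects attribution of cause if that task is given to the assessors. Nor do the documents show that bias occurred or that it favours the mesh; its direction and size are unknown.

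Under the assumed shift to 40% versus 30%, the chance of a false positive favouring the mesh is about five times its nominal value by chi-square (12.1/2.4) and about six times by Fisher (7.7/1.3). This rests on no true effect, a 40% true rate in both arms and 30 patients per arm. The right response is an inexpensive improvement, not a redesign.

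**What to change.** 1. Keep the present composite as the primary outcome.
2. State that the blinded outcome assessors decide whether an obstruction is adhesive and whether a complication is intra-abdominal, from records with the allocation and any description of the mesh removed. This protects attribution only; it cannot recover an intervention that was withheld.
3. Pre-specify one supportive composite from the existing secondary outcomes: any bowel obstruction, whether clinical or on MRI read by the blinded radiologists, regardless of attributed cause or treatment; or fistula. Report it as a relative risk with 95% confidence interval beside the primary result. State any disagreement between the two as a limit on the claim of benefit.

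If the data are already collected, as the past tense of the document suggests, the same work can be done and labelled post hoc.

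The cost is redaction of event records and one extra analysis. The supportive composite will count some milder events and may miss transient obstruction between MRI visits, so it complements the primary outcome and does not replace it. No clinical rule for intervening is proposed.

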#### **Secondary Outcomes**

Secondary outcomes included:

- Individual complication rates, including intraperitoneal adhesions, bowel obstruction, surgical site infection, incisional hernia, and fistula formation

- Time to bowel function recovery, defined as the time to first flatus and tolerance of oral diet
- Length of intensive care unit (ICU) stay and total hospital stay
- Device-related adverse events, including infection, inflammatory reaction, or mesh-related complications
- Radiologic assessment of adhesions or obstruction using magnetic resonance imaging (MRI) at baseline, one month, and two months
- Quality of life assessment using the European Organisation for Research and Treatment of Cancer Quality of Life Questionnaire Core 30 (EORTC QLQ-C30), a validated cancer-specific instrument [20]

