Accordingly, this prospective, multicenter, randomized controlled trial was designed to evaluate the safety and efficacy of Surgicoll-Mesh® as a peritoneal substitute following peritonectomy in patients undergoing CRS for intraperitoneal malignancies. The primary objective was to determine whether the use of a high-purity Type I collagen scaffold reduces the incidence of major postoperative intra-abdominal complications compared with standard peritonectomy closure. Secondary objectives included assessment of individual complication rates, bowel function recovery, length of hospital and intensive care stay, device-related adverse events, radiologic evidence of adhesions, and patient-reported quality of life outcomes using a validated instrument.

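### The only adverse-event outcome is limited to device-related events, which controls cannot have; death, sepsis and deep infection without reoperation are not named for both arms

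*Combined protocol and SAP*

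**What the plan says.** The combined protocol and SAP gives safety equal billing with efficacy. Study Design and Setting describes a trial "evaluating the safety and efficacy of a high-purity Type I collagen-based biomaterial", and the Introduction states the same aim.

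The one outcome labelled as adverse events, under Secondary Outcomes, is "Device-related adverse events, including infection, inflammatory reaction, or mesh-related complications". The Introduction's list of secondary objectives carries the same restriction to device-related events. Under Control Group, patients receive "standard peritonectomy closure without the use of any peritoneal substitute or biomaterial".

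Other harms are outcomes in both arms with no condition on cause. Under Primary Outcome, "The primary outcome was the incidence of major intra-abdominal complications within two months following surgery". Its components are adhesive obstruction needing intervention, enterocutaneous fistula, "Reoperation for intra-abdominal complication", and wound complications of Clavien–Dindo grade 3 or above. Secondary Outcomes adds "Individual complication rates, including intraperitoneal adhesions, bowel obstruction, surgical site infection, incisional hernia, and fistula formation".

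The Statistical Analysis Plan gives general methods: chi-square or Fisher's exact tests for categorical variables, relative risks with 95% confidence intervals for the primary and key secondary binary outcomes (the key ones are not named), and analysis by intention to treat. It has no separate safety analysis. Randomization and Allocation says that the operating surgeon could not be blinded, and that outcome assessors, radiologists and statisticians were blinded where this applied.

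**The concern.** An event can be called device-related only in a patient who has the device. The control count is therefore zero by construction, and the number in the mesh arm has nothing to be set against. It also depends on a causal judgement, and the plan does not say who makes that judgement, by what criteria, or with what knowledge of the arm.

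This matters most for events that an implant in a stripped abdomen could plausibly make more frequent and that extensive surgery or HIPEC could equally explain, such as a collection, a deep infection or sepsis. If such an event is ascribed to the operation, it leaves the device-related count. If it also falls outside the complications listed for both arms, no randomised comparison picks it up. The report could then offer a low device-related count as evidence of safety although the arms were never compared on those events.

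**Working it through.** The plan states no figure for safety, so there is none to reproduce. The first step is a reading of the outcome lists. The second puts numbers on what the present outcome and the proposed one could show.

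**Step 1. Which harms are compared between arms without attribution?**

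| Harm | Named as an outcome in both arms? | Section |
|---|---|---|
| Adhesive obstruction needing intervention | Yes | Primary Outcome |
| Enterocutaneous fistula | Yes | Primary and Secondary Outcomes |
| Reoperation for an intra-abdominal cause | Yes | Primary Outcome |
| Grade ≥3 wound complication | Yes | Primary Outcome |
| Adhesions, bowel obstruction, surgical site infection, hernia | Yes | Secondary Outcomes |
| Inflammatory reaction | Only if device-related | Secondary Outcomes |
| Intra-abdominal infection or collection without reoperation | No, unless recorded as surgical site infection, which is not defined | – |
| Sepsis | No | – |
| Grade ≥3 events outside the complications above | No | – |
| Death | No | – |

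The first five rows are a real randomised comparison of harms. The gap is the last five. The plan also does not say how a death without a prior listed component enters the primary outcome.

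**Step 2. What a zero device-related count would show.** Input: 30 mesh patients (Sample Size Calculation). With 0 events in n patients, the exact upper limit solves (1 − p)^n = tail probability.

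- Two-sided 95%: 1 − 0.025^(1/30) = 0.116, or 11.6%.
- One-sided 95%: 1 − 0.05^(1/30) = 0.095, or 9.5%.
- Chance of seeing at least one event: 1 − 0.95^30 = 79% if the true rate is 5%, and 1 − 0.99^30 = 26% if it is 1%.

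**Step 3. What a both-arm comparison would show.** Input: 30 per arm. The documents give no rates for these events, so the rates below are assumptions. The half-width of the 95% interval for the risk difference is 1.96 × √([p1(1 − p1) + p2(1 − p2)]/30), a normal approximation that is rough at the lowest rates. Power is for an exact Fisher test at two-sided 0.05.

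| Assumed rates | Half-width | Power |
|---|---|---|
| 5% v 15% | 1.96 × √(0.175/30) = 15.0 points | 9% |
| 10% v 20% | 1.96 × √(0.25/30) = 17.9 points | 10% |
| 20% v 30% | 1.96 × √(0.37/30) = 21.8 points | 9% |
| 20% v 40% | 1.96 × √(0.40/30) = 22.6 points | 30% |

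The added outcome would give a fair, unattributed contrast with wide intervals. It would not be a powered test.

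**The case against.** The strongest reply is that the trial already compares harm between randomised arms. The primary outcome is itself a composite of harms, none of which needs a device attribution, and the individual complication rates extend it. An abscess or leak that leads to reoperation counts in the primary outcome whatever its supposed cause. Surgical site infection is not restricted to superficial infection, and the list of individual complications is worded as open-ended. All of this stands. A reader might infer that the trial has no randomised safety comparison at all, and the documents do not support that.

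Two further inferences also go beyond the text. One is that the unblinded surgeon decides which events are device-related. The documents name no one for this, and they state blinding of outcome assessors where it applies. That blinding is hard to reconcile with a judgement that presupposes the device, but what can be said is that the procedure is unspecified. The other is that the plan commits to a between-group test of device-related events. The Statistical Analysis Plan gives generic methods to be used as appropriate and does not name this outcome.

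It is also fair to say that the 0/30 limits show only that 30 patients are few, and that the proposed comparison would suffer from the same small numbers. The case for the change is that the comparison would have a control group and would not depend on attribution; it would not be precise.

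Finally, the document is written in the past tense and the case report forms are not shown. They may already capture these events, or enrolment may be complete.

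**Conclusion.** The point holds as a gap in the safety outcomes. The only adverse-event outcome has no control-arm counterpart and rests on an undescribed attribution. Death, sepsis, grade ≥3 events outside the listed complications, and intra-abdominal infection or collection managed without reoperation are not named for both arms. An excess of these with the implant could go unseen. A safety statement resting on the device-related count alone would be weakly supported: even 0/30 is compatible with a true rate of up to 11.6% (two-sided 95%), and that figure takes every attribution as correct.

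The gap does not undermine the primary comparison, and it does not mean that harms go uncompared. The conclusion rests on two readings: that surgical site infection, left undefined, does not cover every deep infection, and that an outcome the plan does not name is not committed to analysis. The number of such events cannot be estimated from the documents. The plan should be changed on this point; the change is small and leaves the design intact.

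**What to change.** In Secondary Outcomes and the Statistical Analysis Plan, add a safety outcome covering all Clavien–Dindo grade ≥3 events, intra-abdominal infection or collection, sepsis and death through day 60. Record it in both arms with the same definitions, regardless of attribution, and analyse it by intention to treat. Report counts by arm and risk differences with 95% confidence intervals, and label the comparison descriptive.

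Keep device-related events as a summary of the mesh arm only, with an exact confidence interval and no between-group test. State who judges device-relatedness and by what criteria. Do not base the safety conclusion on that count alone.

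The cost is a few more event types on the existing case report forms, at the assessments already scheduled for discharge, day 30 and day 60. If enrolment is complete, the events would have to be abstracted from hospital records, ideally by staff unaware of the arm. The intervals will be wide, about ±15 to ±23 percentage points under the assumed rates, and the report should say so.
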